#### **E. Primary and secondary outcome measures.**

*The outcomes are divided in primary and secondary end-points (Table 3).*

*The primary end-points will consist of:*

1. *Improvement of LVEF after PVC suppression at 12-month follow-up.* This is chosen as primary-end point due to the known prognostic value of LVEF. The lower the LVEF, the higher the risk of sudden cardiac death and heart failure. This will compare the overall improvement or change in LVEF between RFA and AAD groups. This end-point will support that either RFA or AADs have an overall better outcome due to significant improvement of LV function with potential impact on morbidity and mortality associated with PVC-CM.

2. *Responders to PVC suppression strategy at 12-month follow-up* (See rationale under Section “Definitions” in 3rd paragraph of Aim 2). Assessment of the number of responders (delta LVEF  $\geq$  10%) after PVC suppression strategies (RFA or AADs) will assess the effectiveness of RFA and AADs to reverse or improve cardiomyopathy induced by frequent PVCs. Evidence that either RFA or AADs is superior to improve or even reverse LV dysfunction in subjects with high burden PVCs could have significant impact of morbidity and mortality including future heart failure and ventricular arrhythmias, and also may avoid ICD implantation.

*The secondary end-points will consist of:*

1. *Efficacy of RFA vs AADs groups to achieve successful PVC suppression at 12-month follow-up, defined as a reduction of PVC burden  $\geq$ 80% (regardless of LVEF change). Understanding the success rate of PVC suppression between RFA and AADs will help better determine the best treatment to those subjects with high PVC burden.*

2. *Composite end-point of adverse events at 12-month follow-up, including worsening in NYHA functional class (I-IV), number of HF and cardiac-related admissions, RFA complications and AAD adverse effects and cardiovascular death.*

This adverse event composite end-point is chosen to understand the overall complications and adverse effects/events related to RFA and AADs. Worsening of NYHA functional class will be defined as when/if the subject’s functional status worsens by one NYHA class. Hospital admissions will be defined as any visit to ED or hospital admissions related only to a cardiovascular event such as heart failure, angina, pre/syncope and palpitations.

3. *Composite end-point of arrhythmia burden, including PVC recurrence, non-sustained (< 30sec) and sustained (> 30sec) ventricular arrhythmias and arrhythmic sudden cardiac death at 12-month follow-up.* This composite end-point of arrhythmia burden is chosen in order to understand the difference in arrhythmia recurrence between RFA and AAD therapy. PVC recurrence will be defined as reduction of PVC burden  $\leq$  80% at 6- and 12-months when compared to baseline (pre-treatment) PVC burden.

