v. *Treatment – Visit 2.* Using appropriate data collection forms, we will ask that sites obtain current medical therapy information, NYHA functional class and Minnesota HF quality of life questionnaire (QOL). 12-lead ECG should be obtained if clinically indicated. A repeat Zio Patch should be placed to re-assess adequate PVC suppression after RFA or initiation of AADs. The local PI and designated site staff will be able to log in to iRhythm’s ZioReports) 3 weeks later to obtain a Zio Patch Report with repeat PVC burden after intervention. If PVC burden is suppressed by more than 80%, intervention is considered successful and the subject should continue with treatment visits as scheduled,

However, if PVC burden does not decrease by more than 80%, intervention is considered a failure. In such a case, the subject should be considered for a second RFA procedure or a different antiarrhythmic drug depending on the randomization group that the subject was assigned (see Section C: Description of the Intervention/treatment). We discourage crossover of treatment arms since this will result in automatic withdrawal from the study. Nevertheless, subjects that withdraw from the study will be included in a PVC-CM registry if the subject provided consent. (described above Section A.1).

**Figure 1.** PAPS study design. A 3-month Observation (Obs) period allows each subject to serve as their own control to assess benefits of PVC suppression. All subjects will be randomized (R) to either RFA or AADs. OMT, optimal medical therapy. QOL, quality of life questionnaire; NYHA, New York Heart Association class; LVEF, LV ejection fraction; Zio, ambulatory ECG Ziopatch Holter, CMR, Cardiac MRI (\*, visit/intervention if clinically indicated).

vi. *Treatment – Visit 3.* Appropriate data collection forms should be used to collect current medical therapy information, NYHA functional class and Minnesota HF quality of life questionnaire (QOL). 12-lead ECG should be obtained if clinically indicated. A transthoracic echocardiogram should be performed to assess LVEF and a copy mailed to the Echo Core laboratory led by [name] III, M.D. A repeat Zio Patch should be placed to re-assess PVC burden. Local PI and designated site staff will be able to log in to iRhythm’s ZioReports 3 weeks later to obtain a Zio Patch Report if desired for any clinical decision.

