A 2-week ambulatory ECG Holter (Zio Patch, IRhythm, Inc.) will be obtained 4-6 weeks after initiation of AAD to assess whether PVC suppression was successful (defined above). If successful PVC suppression is not achieved, we will ask sites to consider either an increase in the antiarrhythmic dose or change of antiarrhythmic as noted above. A repeat 2-week ambulatory Holter monitor will be done 4 weeks after adjustment of AAD to re-assess PVC suppression.

Radiofrequency Ablation (RFA) of PVCs. RFA will be performed after completion of 3-month observation period). EPS will be performed on their baseline medications, except for antiarrhythmic drugs class II (beta blockers) which will be held at least 5 half-lives prior to procedure. Beta blockers should be resumed after RFA.

EPS and RFA will be performed using standard techniques and protocols similar to those subjects that do not participate in this clinical study. Multipolar electrode diagnostic catheters will be inserted. If no ectopy is present at baseline, isoproterenol may be infused at rates up to 10mcg/min. If the ectopy is infrequent despite adrenergic stimulation, pace mapping will be performed at a pacing cycle length determined by coupling interval of the spontaneous ventricular ectopy. RV or LV PVCs will be mapped/ablated at the discretion of the electrophysiologist. Coronary angiography and/or intracardiac echo will be performed as needed. RFA will be performed at the site of earliest endocardial activation or best pace map. RFA applications will be delivered for at least 30 seconds if adequate power at the electrode-tissue interface is achieved. RFA will be continued for at least 60-120 seconds in sites where PVCs are abolished within 30 seconds. After ablation of the PVCs, isoproterenol will be administered at 2-10 mcg/min as required to shorten sinus CL to 500ms to confirm that PVCs are not inducible by adrenergic stimulation. In the event of polymorphic PVCs, all morphologies are to be targeted for ablation. Subjects will be observed overnight in a telemetry bed and discharged home the next day, as it is current standard of care.

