**Table 3. End-points for PAPS Pilot study**

Primary End-points
- Improvement of LVEF
- Responders to PVC suppression strategy (delta LVEF $\geq$ 10%)
Secondary End-points
- Successful PVC suppression ( $\downarrow$ PVC burden $\geq$ 80%)
- Composite end-point of adverse events 
 
- Worsening NYHA functional class (I-IV)
 
- Number of HF and cardiac-related Hospital admissions
 
- RFA complications / AAD adverse effects
 
- Cardiovascular death
 

- Composite end-point of arrhythmia burden: 
 
- PVC recurrence (PVC reduction < 80 % after RFA or AAD)
 
- Non-sustained and sustained ventricular arrhythmias
 
- Arrhythmic sudden cardiac death.
 

Subjects that refuse enrollment, will be asked to participate in a PVC-CM registry to follow their response and crossover to different treatment strategies (described above Section A.1)..

We hypothesize that subjects and/or physicians will not object to participate due to the 3-month observation period since most tertiary referral centers have significant procedure wait times for which usually they are scheduled between 8- to 12-weeks after clinical decision of PVC suppression is made. We have involved all participating centers, who agree that this is a common and acceptable scenario during which the observation period proposed could take place. In contrast to other clinical studies where RFA is being compared to placebo, we speculate that randomization of RFA vs. AADs will not be an enrollment limitation since all subjects will undergo a PVC suppression strategy. *This pilot study will allow us to prove feasibility of the PAPS study with the current study design including a 3-month observation period and treatment randomization.*

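### The PVC 'recurrence' component of the arrhythmia composite does not require earlier suppression, so subjects who were never suppressed count as recurrences

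*Combined protocol and SAP*

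**What the plan says.** Secondary end-point 3 is a composite of PVC recurrence, non-sustained and sustained ventricular arrhythmias, and arrhythmic sudden death. Section E gives its purpose: it is "chosen in order to understand the difference in arrhythmia recurrence between RFA and AAD therapy".

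- **Recurrence, section E:** "PVC recurrence will be defined as reduction of PVC burden" of 80% or less, "at 6- and 12-months when compared to baseline (pre-treatment) PVC burden".
- **Recurrence, Table 3:** the entry beginning "PVC recurrence (PVC reduction" sets the limit at below 80% after RFA or AAD, with no time point.
- **Secondary end-point 1, section E:** "Efficacy of RFA vs AADs groups to achieve successful PVC suppression at 12-month follow-up, defined as a reduction of PVC burden" of at least 80%.
- **Early non-response, section B, Treatment Visit 2:** "However, if PVC burden does not decrease by more than 80%, intervention is considered a failure". So the protocol already treats early failure as a status of its own.
- **What happens to those subjects:** section H, item 2, encourages poorly suppressed subjects to stay on their assigned arm.
- **Extra recordings:** in section D, for the AAD arm, "A repeat 2-week ambulatory Holter monitor will be done 4 weeks after adjustment of AAD to re-assess PVC suppression". The same section adds a Holter 2 to 4 weeks after a redo ablation.

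Section I says only that secondary outcomes will be analysed in a similar way to the primary ones. It names no at-risk set and no reporting by component for this composite.

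**The concern.** In ordinary use, recurrence means that something went away and came back. The rule tests only the size of the reduction at 6 and 12 months. A subject with a steady 40% reduction on every recording is a recurrence by this rule, although nothing recurred.

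Two different results are therefore mixed: treatment that never suppressed the PVCs, and suppression that was later lost. They mean different things when ablation is compared with drugs. Hypothesis 3 predicts a lower arrhythmia burden with RFA, and section F says the pilot's rates will be used to design and power the large trial. A recurrence rate that is partly or wholly primary failure would mislead that design work. A reader could also take end-points 1 and 3 as two separate pieces of evidence when the PVC component of one is largely the other in reverse.

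**Working it through.** The plan gives no figure for this end-point, so there is none to reproduce. The check applies the definitions as written.

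**1. One recording, three rules**

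| Reduction from pre-treatment | Success (end-point 1, ≥80%) | Recurrence (section E, ≤80%) | Recurrence (Table 3, <80%) |
|---|---|---|---|
| 0%, 50%, 79.9% | no | yes | yes |
| exactly 80% | yes | yes | no |
| 80.1%, 100% | yes | no | no |

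At any single visit, recurrence is the reverse of success, apart from the tie at 80% in section E.

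**2. Two visits: either or both?**

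| 6 months | 12 months | Recurrence if either | Recurrence if both | End-point 1 |
|---|---|---|---|---|
| <80% | <80% (never suppressed) | yes | yes | failure |
| ≥80% | <80% (late relapse) | yes | no | failure |
| <80% | ≥80% | yes | no | success |
| ≥80% | ≥80% | no | no | success |

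Never-suppressed subjects count under both readings. Under *either*, every 12-month failure of end-point 1 is also a recurrence. Under *both*, a subject suppressed at 6 months who relapses by 12 months is missed.

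**3. Size in one arm.** Section I plans 19 to 20 subjects per arm. The Protection of Human Subjects section puts single-procedure RFA success above 80%, so up to about 0.20 × 20 = 4 subjects could be unsuppressed before any redo. With assumed counts in an arm of 20:

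- 4 never suppressed, 0 relapse: rule as written 4/20 = 20%; relapse among those suppressed 0/16 = 0%.
- 4 never suppressed, 2 relapse: rule as written 6/20 = 30%; relapse among those suppressed 2/16 = 12.5%.

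**4. Size between arms.** Assume 12-month success of 80% with RFA and 50% with AADs, and no relapse in anyone. The rule gives 20% against 50%, a ratio of 0.20/0.50 = 0.40, although true relapse is zero in both arms.

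**5. Does the whole composite repeat end-point 1?** Let *s* be 12-month success and *q* the probability that a suppressed subject has another component event. Using 12-month status only, the share of composite events that are end-point 1 failures is (1 − s)/[(1 − s) + s·q]. For s from 0.50 to 0.80:

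- q = 0: 100%
- q = 0.1: 71% to 91%
- q = 0.3: 45% to 77%
- q = 0.5: 33% to 67%

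The plan gives neither *s* nor *q*, so the overlap is undetermined.

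**6. Extra recordings.** Table 2 schedules four post-treatment Zio recordings (Treatment Visits 2, 3, 4 and 6). If runs on any recording count, and each recording shows a run with assumed probability *p*, independently, the chance of at least one is 1 − (1 − p)⁴ on the schedule and 1 − (1 − p)⁵ with one added recording:

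- p = 0.1: 34% and 41%
- p = 0.2: 59% and 67%
- p = 0.5: 94% and 97%

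One extra Holter adds 3 to 8 percentage points in these cases, and only in subjects whose treatment was adjusted or redone. PVC recurrence itself is fixed at 6 and 12 months and is not affected.

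**The case against.** The strongest reply is that the fault lies mainly in a label. The end-point is headed arrhythmia burden and the analysis is by intention to treat, so counting a subject with a persistently high PVC burden as an event is defensible. Early failure is recorded separately at Treatment Visit 2, so the data can separate the two states. This is a secondary end-point in a small pilot, and the Data Sharing Plan says the pilot is not meant to settle the relative benefit of the strategies. Exactly 80% on a continuous measure will be rare.

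Most of this stands, and it shapes the fix: never-suppressed subjects should remain events. It does not rescue the wording, because the stated purpose is recurrence and no planned table separates failure from relapse.

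Three stronger readings are tempting, and the documents do not support them.

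- *The whole end-point largely repeats secondary end-point 1.* Only the PVC component does, and containment of every 12-month failure requires the *either* reading. For the composite, the overlap runs from 33% to 100% over assumed rates.
- *Non-sustained runs will swamp the comparison.* With the run probabilities of 34% to 94% from step 6 and the success rates of step 4, the composite ratio 1 − s(1 − q) between arms moves from 0.40 to between 0.71 and 0.98. Every input is assumed, including equal run rates in the arms and independence. The plan gives no rate and does not say which recordings count. This would also be dilution, the opposite of duplication.
- *Only true relapses belong in the composite.* That would score never-suppressed subjects as free of PVC events. With 80% and 50% ever suppressed and 20% relapse in each arm (assumed), the component becomes 0.80 × 0.20 = 16% with RFA and 0.50 × 0.20 = 10% with AADs, so the arm that suppresses more looks worse.

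**Conclusion.** The concern holds for the PVC component. Neither section E nor Table 3 requires earlier suppression, while sections B and H identify failures and keep them in follow-up, so never-suppressed subjects are counted as recurrences. This follows from the text alone and holds whether one or both time points are needed. The either-or-both ambiguity, the mismatch between ≤80% and <80%, and the possible outcome-dependent detection of non-sustained runs are real but smaller.

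The size is illustrative: 20% apparent recurrence against 0% true recurrence if 4 of 20 are never suppressed and none relapse. Overlap of the full composite with end-point 1 cannot be fixed from the documents. The primary end-points are not affected. The change is worth making before the data are analysed, because the pilot's rates are meant to inform the large trial.

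**What to change.** Amend the Synopsis, section E and Table 3, and add the tabulation to section I.

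1. **Name and rule.** Call the component PVC non-suppression or recurrence. Count a reduction below 80% at Treatment Visit 4 or Treatment Visit 6, stating that either is enough. Never-suppressed subjects stay in as events.
2. **Exclusive states, by arm,** among randomised subjects who started treatment:
   - never suppressed: no post-treatment recording, scheduled or after re-treatment, with a reduction of at least 80%;
   - suppressed then recurred: at least 80% on any earlier recording and below 80% at a later Treatment Visit 4 or 6;
   - sustained suppression, with suppression first seen at Treatment Visit 6 shown apart as late suppression;
   - not assessable.

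   List subjects withdrawn at week 12 before treatment separately. Show the states together, and do not present recurrence among suppressed subjects alone as a randomised comparison, because that group is formed after randomisation.
3. **One threshold.** Use at least 80% for success and below 80% for failure in all end-point definitions. The Treatment Visit 2 wording, which also guides re-treatment, differs from section D on exactly 80%; the sponsor should reconcile those passages.
4. **Arrhythmia components.** Count non-sustained runs on scheduled Zio recordings only and show them beside the pre-treatment recording. Count sustained arrhythmia and sudden death whenever they occur. Report each component separately.

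The scheduled recordings are already in Table 2 and those after re-treatment in section D, so no new data are needed. The cost is a wording change, a little more tabulation, and some non-sustained runs on unscheduled recordings left uncounted.

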**F. Data interpretation and analysis**

**Barriers / limitations of enrollment, randomization and retention of participants in this clinical pilot study.**

Subjects are referred to tertiary centers for RFA of PVCs in subjects with associated CM in the hope to reverse LV dysfunction if the underlying cause is related to PVC-CM. Thus, it is important to understand that the observational period and randomization is acceptable and will not compromise enrollment. Subjects that meet inclusion and exclusion criteria will be asked to participate. We plan to understand the comfort level of subjects participating in this clinical study. We will assess the rate and rationale for declining participation or withdrawal from this study. Those individuals that decline or withdraw will be asked to provide one of the following rationale: 1) uncomfortable with observation/waiting period, 2) uncomfortable with AAD therapy, 3) unable/unwilling to commit for a long term follow up, 4) uncomfortable participating in any type of research, 5) other reasons including those not related to the study itself.

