**Definitions:**

The *diagnosis criteria for PVC-CM* is based on LVEF  $\leq$  45% (by echocardiography) and average PVC burden  $\geq$  10% in an ambulatory ECG Holter monitor that meet the inclusion and exclusion criteria (Table 1), regardless of severity and time of onset. LVEF and PVC burden must be within 150 days of Enrollment Visit (Day 0).

*Responders are defined as an LVEF increase greater than 10% points regardless of intervention.*

If screening confirms eligibility (LVEF  $\leq$ 45% and PVC burden  $\geq$  10%), a baseline visit will be scheduled to obtain subject's demographics and medical history, 12-lead ECG, Minnesota living with HF quality of life (QOL) questionnaire, NYHA functional class and cardiac magnetic resonance (CMR) if clinically indicated. Subjects that refuse enrollment, will be asked to participate in a PVC-CM registry to follow their response and crossover to different treatment strategies.

If subjects meet inclusion criteria (Table 1) during screening, informed consent should be obtained. Stratified randomization to either RFA or AADs will be performed at the time of enrollment (baseline visit, week 0). Based on our preliminary data, we expect that around 30% of subjects will have a PVC burden  $>$ 20%. Thus, a *stratified randomization based PVC burden (assessed by Holter) above and below 20% is needed to assure that subjects in both groups (RFA vs. AAD) are equally distributed between PVC burden above and below 20%.* Stratified randomization will be performed using approved software available at the Coordinating Center only.

If a subject is randomized to the RFA arm, a RFA procedure (Visit 1) should be scheduled at the time of randomization due to usual 8-week next available RFA appointment in most participating centers. Yet both, RFA and AAD interventions should only occur or be initiated after completion of a 3-month observation (Table 2 - Visit Tx-V1, week 12-15).

A 3-month observation period will assess spontaneous variation of PVC burden and improvement or deterioration of LV function. During the final 3-month observation visit (Week 12), LVEF and Holter will be repeated to confirm eligibility if PVC burden and LVEF remains  $\geq$ 10% and  $\leq$ 45%, respectively.

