### **H. Limitations**

The following limitations may arise during the development of this project:

1. Subjects with progression from mild and moderate to severely symptomatic PVCs (incapacitating palpitations and dizziness) will be encouraged to complete the 3-month observation period since PVC suppression will initiate immediately thereafter. Subjects are excluded if symptoms preclude completion of the 3-month observation.
2. Limited or poor suppression of PVC suppression in randomized treatment (RFA or AAD) arm. These subjects are encouraged to remain on the assigned arm. However, crossover to the alternate treatment arm can be considered after 6 months only if considered medically indicated. If crossover were to occur before 6 months, immediate notification and final evaluation with echocardiogram and ambulatory ECG Holter monitor (Zio Patch) should be obtained prior to crossover, and the subject will be excluded from study and followed in a PVC-CM registry if consent was provided (described above Section A.1).
3. PVC variability or spontaneous resolution of PVCs may limit pre vs post procedure comparison. PVC burden has significant temporal variability and it may be a major limitation in the study of arrhythmias. Schmidt demonstrated that an 80% absolute reduction of PVC burden is required to show a true drug effect. To minimize daily PVC variability, PVC evaluation in this study will be performed using a 2-week ambulatory ECG Holter monitor (Zio Patch, IRhythm, Inc.) which is shown to be a better indicator of long-term PVC burden.
4. LV function assessment in ventricular bigeminy. Assessment of LVEF during frequent PVCs represents a challenge for all imaging modalities. Modified acquisition and post-processing methods have been developed to correct for R-R interval variability expected with frequent PVCs. In the event that the subject has persistent ventricular bigeminy at the time of the scheduled echocardiography, the LV function assessment should be postponed for a few hours or a later date when PVCs are less prominent (at least ventricular quadrigeminy).

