##### ***Characteristics of the subject population, including their anticipated number, age range, and health status if relevant.***

We will include subjects of any race, ethnic group, gender and adult age (18 years or older) with frequent PVCs (defined as PVC burden  $\geq 10\%$  by at least a 24-hr ambulatory Holter) ) and LV dysfunction (LVEF  $\leq 45\%$ ) without any clear reversible cause of CM (Study Design – Part I: Table 1). All subjects that meet inclusion/exclusion criteria will be offered participation in this study regardless of gender, age or ethnic background. We will attempt to have diversity in age, gender and ethnicity in our study by involving the general population treated in different University Hospitals, even though, there is no evidence that age, gender or ethnic groups will respond differently to treatment arms. While most subjects will be asymptomatic (no palpitations), the degree of heart failure symptoms will be variable (none to moderately severe). Based on sample size estimates, the full scale PAPS study will require 140 subjects randomized to either RFA (70 subjects) or AAD therapy (70 subjects) to assess differences between RFA and AAD treatments (see Sample size justification Section in Study Design – Part I). However, we propose a pilot study of 36-39 subjects (20% of subjects) to determine acceptability of treatment randomization of RFA versus AADs, rate of spontaneous recovery of CM and PVCs, responders, adverse events and treatment crossover, and to assess the feasibility of enrolling, randomizing and retaining participants. This pilot study will allow us to better design and power the large prospective PAPS study.

In addition, we propose to screen all consecutive subjects undergoing at least a 24-hr, ambulatory ECG Holter for frequent PVCs ( $\geq 10\%$  burden) and LVEF  $\leq 45\%$ . This has the intention to better estimate the prevalence of PVC and CM in this specific population.

No vulnerable populations, such as fetuses, neonates, pregnant women, children, prisoners, institutionalized individuals, or others who may be considered vulnerable populations will be enrolled in our study.

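### The one-choice list of reasons for declining or withdrawing has a code for reluctance about AADs but none for reluctance about RFA, so coded reasons cannot be compared evenly between the two treatments.

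*Combined protocol and SAP*

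**What the plan says.** The list is in Part I, Section F, under the barriers to enrollment, randomization and retention. Its purpose is stated there: "We will assess the rate and rationale for declining participation or withdrawal from this study". The instruction is single-choice and covers both groups: "Those individuals that decline or withdraw will be asked to provide one of the following rationale". Codes 1 to 3 are "uncomfortable with observation/waiting period, 2) uncomfortable with AAD therapy, 3) unable/unwilling to commit for a long term follow up". The list ends with "4) uncomfortable participating in any type of research, 5) other reasons including those not related to the study itself". No free text or sub-coding of code 5 is described.

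The question that the list serves is set out in several places. Aim 1 in the Specific Aims is the feasibility of enrolling, randomizing and retaining. The Protection of Human Subjects section, on the characteristics of the population, says that the pilot is meant "to determine acceptability of treatment randomization of RFA versus AADs". Section F, after Table 3, gives only an expectation on this point: "we speculate that randomization of RFA vs. AADs will not be an enrollment limitation".

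On timing, Section A (Definitions) states: "Stratified randomization to either RFA or AADs will be performed at the time of enrollment". Treatment starts at weeks 12 to 15 (Table 2), so a subject knows the assigned arm for about three months before receiving it.

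**The concern.** The pilot asks whether people will accept being randomised between an invasive procedure and a drug. The tool for recording why they refuse or leave has a code for dislike of the drug and none for dislike of the procedure. Someone who would accept only RFA fits code 2. Someone who would accept only drugs has no matching code and joins code 5, together with reasons that have nothing to do with the study.

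Tabulated as written, the list could show AAD therapy as the only treatment that people object to, because it is the only one that can appear by name. The team planning the full-scale trial would then lack half of the information on treatment acceptability that the pilot was set up to supply.

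**Working it through.** **Figures in the plan.** The plan attaches no figure to this point. Its one reproducible design figure is the full-scale sample size in the sample size justification. Inputs: difference 5 points (40% against 35%), SD 10, power 0.80, type I error 0.05 (two-sided assumed), 10% dropout. Per group, n = 2(1.96 + 0.84)² × 10² / 5² = 62.7, rounded up to 63; 63 / 0.9 = 70; total 140, as stated. Nothing in it depends on the reason list.

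**Step 1. Where each reason goes.**

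| Reason given | Code | Separable in a table? |
|---|---|---|
| Waiting period | 1 | Yes |
| Reluctance about AADs | 2 | Yes |
| Long follow-up | 3 | Yes |
| Any research | 4 | Yes |
| Reluctance about RFA | 5 | No |
| Unrelated to the study | 5 | No |

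**Step 2. What the table can then show.** Let n be the people giving a reason, a the number choosing code 2, and o the number choosing code 5. The share citing AADs is a/n. The share citing RFA is known only to lie between 0 and o/n. Illustration with assumed counts: of 20 people, 6 object to AADs and 6 to RFA. AADs show as 6/20 = 30%. RFA does not appear by name. Code 5 holds at least 6/20 = 30%, and a reader can say only that RFA accounts for some part of it, from none to all.

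**Step 3. Is RFA reluctance plausible here?**
- The Risk Benefit assessment in Section J lists stroke, tamponade and death among the RFA risks.
- Section L expects most subjects to come from Part II Holter screening.
- The population description expects most to be without palpitations.
- In the survey reported under Significance, for an asymptomatic patient with LVEF 45%, 29.9% of electrophysiologists chose RFA and 50% chose conservative management. These are physicians' choices, so this is indirect.

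**Step 4. Does another described record hold the reason?** For a decliner, no: there is no adverse event form, and the data items of the PVC-CM registry (Section A.1) do not include the reason for refusal. A subject assigned to RFA at week 0 who leaves before the procedure may have neither an adverse event nor a crossover, and no other described form asks why.

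**Step 5. Scale.** The 10% dropout is an assumption of the sample size simulation, borrowed here for scale. 0.10 × 36 = 3.6 and 0.10 × 39 = 3.9, so about 4 withdrawals, or 1.8 to 1.95 per arm. One RFA-related reason under code 5 would be 1/4 = 25% of them. With so few, percentages are very loose even with a perfect list. The exact 95% interval for 0 of 4 runs from 0 to 1 − 0.025^(1/4) = 60%, and for 1 of 4 from 0.6% to 81%. The number of decliners is not given.

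**The case against.** The strongest reply is that code 5 is open to study-related reasons, so RFA reluctance is recorded, and a large catch-all would be visible in the table. That is right as far as it goes: the reason is kept but cannot be told apart. The data collection forms and the Manual of Operations are not among the documents, so free text may exist there; the protocol does not describe it.

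A second reply is that Section F describes candidates as referred for RFA, so AAD reluctance is the barrier that matters. Section L weakens this, since it expects most subjects from Holter screening.

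A reader might infer more than the documents support:

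- *That withdrawals for adverse effects or failed suppression are lost.* They have no code of their own, but this holds for both arms equally and creates no tilt. They are also largely recoverable. Section C (c.6) and Section D document events and side effects, the serious adverse event form records whether the subject was withdrawn, and the adverse event form has a code for permanent discontinuation. Crossover is tracked in Sections F and H.
- *That the retention data as a whole are biased by arm.* Counts of withdrawals by arm do not depend on the list. Decliners have no arm, because consent comes before randomization; for them the imbalance is by treatment named.
- *That symptoms during observation have no place.* Section H says "Subjects are excluded if symptoms preclude completion of the 3-month observation", which repeats an exclusion criterion. A subject who later finds the wait intolerable may fit code 1.

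**Conclusion.** The point holds in a narrow form. Reasons for declining or withdrawing are coded by treatment for AADs only, so they cannot be compared evenly between the two treatments, although acceptability of that randomisation is something the pilot says it will determine. The information most at risk is the reason of a decliner, or of an RFA-assigned subject who leaves before the procedure, because no other described record holds it.

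The size is minor. No rate, sample size, error rate or stated feasibility threshold changes. About 4 withdrawals are expected if the 10% dropout assumption carries over to the pilot. The conclusion assumes that the list is used as written, with one reason per person and code 5 not subdivided. The 20-person illustration is assumed and is not evidence of how many people would object to RFA.

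**What to change.** In Section F:

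- Add a code parallel to code 2: *uncomfortable with RFA / invasive procedure*.
- Split code 5 into *other study-related reason (specify)* and *unrelated to the study*.
- Tabulate reasons for decliners overall and for withdrawals by assigned arm. With about 4 withdrawals, show counts rather than percentages alone.
- For withdrawals linked to an adverse effect, or to inadequate suppression with crossover, link to the adverse event and crossover records already kept instead of collecting the same facts again.

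The cost is a slightly longer form and one table. No visit, test or sample size changes.
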